1.0 BACKGROUND

1.1 Device Name

The Preceptis Hummingbird® Tympanostomy Tube System (H-TTS)

1.2 Device Description

The Hummingbird® Tympanostomy Tube System (H-TTS) is a disposable surgical tool designed to deliver a tympanostomy tube ("ear tube") into the tympanic membrane of patients during a tympanostomy tube placement procedure.

More than 1,000,000 ear tubes are inserted annually in the US, making it one of the most common surgical procedures performed in children. Most ear tubes are inserted by otolaryngologists using either local anesthesia (usually adults) or general anesthesia (usually children).

Preceptis Medical, Inc. has developed the H-TTS to reduce trauma, pain, and risk to the patient while reducing the overall surgical procedure time. The H-TTS integrates the multiple surgical instruments necessary for current surgical procedure into a single, one-pass device. The H-TTS creates an incision in the tympanic membrane ("ear drum") and inserts a tympanostomy tube with the push of a lever. Thus, the H-TTS allows placement of a tympanostomy tube with a single pass down the ear canal. The ear tube used with the H-TTS is a standard, commercially available tympanostomy tube.

1.3 Summary of Previous Clinical Results

285 patients have been treated in an OR or ASC under GA or sedation as part of two prior clinical studies at the University of Minnesota Masonic Children's Hospital, Children's Hospitals and Clinics of Minnesota, and Mayo Clinic. Procedural outcomes and feedback from the otolaryngologists have shown that the H-TTS reduces surgical trauma for the patient as designed. Safety was evaluated by two independent otolaryngologist reviewers, and no safety issues were identified. There were no intra-operative or immediate post-operative adverse events.

Additionally, a feasibility study was initiated in 2017 in up to 20 patients at Health Partners with [name] as the PI. The study is evaluating the intra-operative performance of the H-TTS in children from 6-60 months. Twelve (12) children were enrolled in the feasibility study and treated successfully in an office setting with the H-TTS and only local anesthetic. There have been no intra-operative adverse events. Using the H-TTS in an office may be even safer than under sedation or a standard tube procedure under GA since the child's movement can be mitigated in the office environment. Under sedation, there is still some minor movement, and, under GA, patients can still move from a painful stimulus and are frequently restrained with induction or wake up. Due to the positive results of the feasibility study patients, the decision was made to proceed to a larger multi-site assessment.

Enrollment of 225 children (209 6-24 months and 16 5-12 years), for a total of 437 ears have been completed in this Pivotal Clinic Study. Study enrollment was allowed to surpass the goal of 200 enrollments to allow collection of FDA requested patient tolerability videos in the 6-

24 month old group and to give study investigators access to office tube placement due to limited operating room availability during the COVID-19 pandemic. The study results demonstrate the safety, efficacy and tolerability of in-office tube placement in young children using the HTTS, patient restraint, and topical anesthetic. Tubes were successfully placed in the office in 98.9% of the cases (success); the anticipated AE rate was 0.46% and there were no serious AEs reported (safety); and the HTTS successfully delivered the tube across the TM in 97.0% of the ears (efficacy).

1.4 Regulatory Status

The H-TTS has been cleared by the FDA under the following conditions:

- In adults, the H-TTS is cleared for use in any location with any type of anesthetic.
- In children, the H-TTS is cleared for use in a hospital or ASC setting under both general anesthesia and moderate (conscious) sedation.
- In children 6-24 months, the H-TTS is cleared for use in an office setting.

1.5 Indications for Use and Intended Use

The H-TTS is intended to deliver a tympanostomy tube (also referred to as a ventilation tube) through the tympanic membrane of the patient and is indicated to be used in office settings for children 6-24 months old.

2.0 STUDY OBJECTIVES

The objective of this study is to evaluate the safety and performance of the H-TTS for the placement of ear tubes in children 2-21 years old undergoing tympanostomy tube placement in an otolaryngology clinic using local anesthetic and control of patient movement, as applicable.

3.0 STUDY DESIGN OVERVIEW AND DURATION

The study is a continuation of a multi-site, prospective, treatment-only study of the H-TTS to enroll patients 2-21 years old. Enrollment is complete for the 6-24 month old group.

Enrollment in the study at each site will begin after receipt of Institutional Review Board (IRB) approval. The goal is to enroll 30 patients in the 2-4 year old group and 30 patients in the 5-21 year old group at up to 10 clinical sites.

4.0 STUDY ENDPOINTS

4.1 Safety Endpoint

The rate of AEs, and the rates for each specific type of event, will be analyzed.

4.2 Efficacy Endpoint

Efficacy evaluation will consist of determining whether the H-TTS device successfully delivers the tympanostomy tube across the tympanic membrane.

4.3 Success Criteria

Success will be defined as the ability of the surgeon to place ear tubes using the H-TTS device in the office setting with the use of local anesthetic.

5.0 STATISTICAL METHODS AND DATA ANALYSIS

5.1 Data Analysis

Data from the study will be analyzed on an as-treated basis using a common closing date. Standard summary statistics will be calculated for all study outcome variables. Categorical data will be summarized in frequency distributions. Detailed summaries of all adverse events will be provided.

The analysis outlined below will be completed first on all subjects aged 2 to 21 years (N=60) and then separately for the subgroups of 2 to 4 years (N=30) and 5 to 21 years (N=30).

The rate of adverse events and the delivery success rate will be calculated, along with corresponding 95% exact confidence intervals which will be calculated using the Clopper-Pearson method.

The adverse events of interest are primarily those specific to the delivery of the tube. These events are acute extrusion of the tube and tube displacement into the middle ear. The proportion of ears experiencing one of these adverse events will be calculated and an exact 95% confidence interval will be constructed about that estimate. These data will be compared heuristically to published AE rates, in particular, to those found in Kay et. al. (2001) who performed a meta-analysis on tympanostomy tube sequelae and to Steele et. al. (2017) published in AHRQ which provides incidence rates for the adverse events of interest. From these two sources of information an expected adverse event rate of 4.5% of ears treated is anticipated. Since the adverse events of interest can also be summarized on a subject basis, the proportion of subjects experiencing an adverse event will also be calculated and 95% exact confidence intervals about that proportion provided. Again, these estimates and confidence intervals will be done separately for each event type.

The proportions of successfully delivered tubes will be calculated, along with the corresponding 95% exact confidence intervals which are constructed using the Clopper-Pearson method. This estimate is on a per ear basis.

The proportion of successful procedures will also be summarized on a per subject basis. A successful subject will be one who has both ears successfully treated. Again, exact 95% confidence intervals will be provided.

Study success will be determined based on a qualitative clinical analysis of all data.

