5.2 Enrollment

A patient will be considered enrolled after informed consent is signed and the incision is made in the tympanic membrane and delivery of the ear tube is attempted with the H-TTS. Inclusion and exclusion evaluation will not require baseline testing and will thus be evaluated prior to signing the consent.

Enrollment may begin when the following criteria are met:

- IRB approval of the study protocol and informed consent documents.
- Signed Investigator Agreement-Clinical Study Agreement.

- Investigational site personnel training on the study protocol.
- Inclusion-exclusion criteria met for each patient.

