7.1 Inclusion Criteria

Patients must meet all of the following:

- 1. Scheduled to undergo tympanostomy tube insertion in the clinic.
- 2. Children 2 to 21 years old.
- 3. Signed parental consent and child assent documents as applicable.
- 4. Parent is fluent in English

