7.2 Exclusion Criteria

Patients will be excluded should they meet any of the following:

- 1. Any condition that, in the opinion of the investigator, may place the subject at greater risk (e.g., child with developmental delay).
- 2. Anatomy precludes sufficient visualization and access to the tympanic membrane.

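### The per-subject success rule in 5.1 requires both ears, so an eligible child treated successfully in one ear counts as a failure if the rule is applied as written (minor)

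*Combined protocol and SAP*

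**What the plan says.** Section 5.1 plans a per-ear delivery rate and then adds a subject-level summary: "The proportion of successful procedures will also be summarized on a per subject basis". The rule for that summary is "A successful subject will be one who has both ears successfully treated", with an exact 95% interval. The section gives no rule for a child with one treated ear and does not limit the denominator to children treated in both ears. It also states an analysis basis: "Data from the study will be analyzed on an as-treated basis using a common closing date".

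Nothing elsewhere requires two ears:

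- The relevant inclusion criterion in 7.1 is "Scheduled to undergo tympanostomy tube insertion in the clinic".
- The two exclusions in 7.2 concern greater risk to the child and anatomy ("Anatomy precludes sufficient visualization and access to the tympanic membrane").
- Under 5.2 a consented patient is enrolled once "the incision is made in the tympanic membrane and delivery of the ear tube is attempted with the H-TTS", and one ear is enough for that.
- The success criterion in 4.3 names no number of ears.

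The precision tables in 6.0 nevertheless pair 60 subjects with 120 ears and 30 subjects with 60 ears, that is, two ears per child. Section 1.3 describes the part of the study already completed: "Enrollment of 225 children (209 6-24 months and 16 5-12 years), for a total of 437 ears".

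**The concern.** A child who needs a tube in one ear can enter the study, receive it successfully, and still not meet the definition of a successful subject. Each such child lowers the per-subject rate although no delivery failed. If the analyst decides not to follow the sentence literally, 5.1 does not say whether the child is judged on the treated ear or left out of the denominator, and in an open single-arm study that choice would be made with the results in view.

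What is at stake is the accuracy of one descriptive proportion and its interval, overall and in each age subgroup. Study success is to be judged qualitatively from all the data, and this proportion is part of those data.

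**Working it through.** **Interval method.** Section 5.1 specifies "95% exact confidence intervals which will be calculated using the Clopper-Pearson method". For x successes in n, the lower limit is the 2.5% quantile of Beta(x, n − x + 1) and the upper limit is the 97.5% quantile of Beta(x + 1, n − x).

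**The plan's own figures.** Section 6.0 gives intervals for 95% delivery success per ear.

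- 114/120: 89.43–98.14, width 8.71. The plan states 89.4–98.1, width 8.7.
- 57/60: 86.08–98.96, width 12.88. The plan states 86.1–99.0, width 12.9.

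Both are reproduced. The plan gives no expected value or interval for the per-subject rate.

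**One-ear children in the completed part (1.3).** With one or two ears per child, the number is 2 × 225 − 437 = 13. The share is 13/225 = 5.8% (exact 95% interval 3.1–9.7). Two-ear children number 225 − 13 = 212.

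**Ceiling under the literal rule.** With k one-ear children among N, the highest attainable per-subject rate is (N − k)/N. For the completed part this is 212/225 = 94.2% (90.3–96.9), even if every treated ear succeeded. This is a hypothetical ceiling. The 98.9% of cases quoted in 1.3 matches 432/437 ears and no whole number out of 225 children, so it does not show how a per-subject rule was applied.

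**Planned cohort, every treated ear successful.** The value of k at ages 2–21 is not given, so a range is shown.

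| N | k (assumed) | Literal rule | All treated ears |
|---|---|---|---|
| 60 | 0 | 60/60 = 100% (94.0–100) | the same |
| 60 | 1 | 59/60 = 98.3% (91.1–99.96) | 60/60 = 100% (94.0–100) |
| 60 | 3 | 57/60 = 95.0% (86.1–99.0) | 60/60 = 100% (94.0–100) |
| 60 | 6 | 54/60 = 90.0% (79.5–96.2) | 60/60 = 100% (94.0–100) |
| 30 | 2 | 28/30 = 93.3% (77.9–99.2) | 30/30 = 100% (88.4–100) |

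If the 5.8% share carried over (an assumption), the expected k would be 0.0578 × 60 = 3.5 overall and 0.0578 × 30 = 1.7 per subgroup. The chance of at least one one-ear child would be 1 − (1 − 0.0578)^60 = 97% and 1 − (1 − 0.0578)^30 = 83%.

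**One real failure, in a two-ear child (N = 60, k = 3 assumed).**

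- Literal rule: 56/60 = 93.3% (83.8–98.2).
- One-ear children left out: 56/57 = 98.2% (90.6–99.96).
- Judged on treated ears: 59/60 = 98.3% (91.1–99.96).

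If the failure is in a one-ear child instead, the last two become 57/57 = 100% and 59/60 = 98.3%.

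**The case against.** The strongest reply is that the literal reading is unlikely to be the intended one. Section 5.1 opens with an as-treated basis, 4.3 sets no number of ears, and 6.0 works with two ears per child, so the reference to both ears may be shorthand for the usual bilateral case. This is plausible, and nothing in the documents shows that the sponsor would score a successful one-ear child as a failure. But the as-treated sentence does not redefine the success rule, and no other section does. The rule as it stands gives the wrong result for these children.

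A second reply is that little depends on the number. That stands. Efficacy is device delivery, estimated per ear; the per-subject rate is an additional summary with no test or threshold. The two non-literal readings also differ little: by 0.1 point, or by 1.7 points if the failure is in a one-ear child. Only the literal reading moves the result noticeably.

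A reader might go further and infer that the whole 5.8-point gap in the completed part is case mix and says nothing about the device or procedure. The documents do not support that. Some of the 13 children may have had a planned second ear that was not attempted, and counting those as unsuccessful could be defended. The part of the gap due to the rule is therefore unknown, between 0 and 5.8 points. Nor do the documents show that the rule was applied to that cohort.

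**Conclusion.** Wrong as written, and minor. The both-ears rule does not fit a population that may include one-ear children, and followed literally it caps the per-subject rate at (N − k)/N. That such children can enter is clear from 5.2, 7.1 and 7.2. That 13 were treated in the completed part rests on one or two ears per child.

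The size in the planned cohort is uncertain. It is zero with no one-ear children, 1.7 points with one of 60, and 5.0 points with three of 60 when every treated ear succeeds. The completed part was mostly children aged 6–24 months (209 of 225), so its one-ear share need not hold at ages 2–21.

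It would be an overstatement to say that the efficacy or safety result is biased. The per-ear delivery and adverse-event estimates do not use this rule.

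**What to change.** Reword the sentence in 5.1 along these lines: *A successful subject is one in whom every treated ear (one or two) was successfully treated.* State that ear-level success has the same definition as in the per-ear analysis, and that a treated ear is one in which delivery with the H-TTS was attempted, so that a failed attempt stays in the count. Report the numbers of one-ear and two-ear subjects beside the rate, overall and by age subgroup. This keeps the as-treated basis and settles both numerator and denominator before analysis.

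The cost is two or three sentences and no extra patients or data.

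Under this wording, a child with one successful ear and a planned second ear that was not attempted counts as a success. If intended ears are already recorded, those children can optionally be listed, or the rate shown a second time with them counted as not successful. The case report forms are not reproduced, so whether intended ears are recorded cannot be judged; the main fix does not depend on it.

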5.2 Enrollment

A patient will be considered enrolled after informed consent is signed and the incision is made in the tympanic membrane and delivery of the ear tube is attempted with the H-TTS. Inclusion and exclusion evaluation will not require baseline testing and will thus be evaluated prior to signing the consent.

Enrollment may begin when the following criteria are met:

- IRB approval of the study protocol and informed consent documents.
- Signed Investigator Agreement-Clinical Study Agreement.

- Investigational site personnel training on the study protocol.
- Inclusion-exclusion criteria met for each patient.

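### Enrollment starts only at incision and attempted delivery, so an eligible, consented child stopped earlier appears to drop out of the per-subject success rate

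*Combined protocol and SAP*

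**What the plan says.** Section 5.2 sets the point of enrollment: "A patient will be considered enrolled after informed consent is signed and the incision is made in the tympanic membrane", with attempted H-TTS delivery as a further condition in the same sentence. It also places the eligibility check before consent: "Inclusion and exclusion evaluation will not require baseline testing and will thus be evaluated prior to signing the consent".

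Section 5.1 gives the analysis basis: "Data from the study will be analyzed on an as-treated basis using a common closing date". Its analysis numbers are 60 overall and 30 in each age group. These equal the target in section 3.0: "The goal is to enroll 30 patients in the 2-4 year old group and 30 patients in the 5-21 year old group".

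Two statements concern success for a child. Section 5.1 says "A successful subject will be one who has both ears successfully treated". Section 4.3 says "Success will be defined as the ability of the surgeon to place ear tubes using the H-TTS device in the office setting", with local anesthetic. Neither names a denominator. The overall conclusion is left to judgment: "Study success will be determined based on a qualitative clinical analysis of all data".

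Several steps come before the incision: control of movement and topical anesthetic (section 9.0), and wax removal where needed (section 11.1.3.1).

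**The concern.** A child can be judged eligible, have consent signed, be brought to the procedure room, and then be stopped because the child cannot be kept still or cannot tolerate the anesthetic or wax removal. In that child the surgeon was not able to place tubes in the office under local anesthetic, which is what section 4.3 is about. Under section 5.2 the child was never enrolled, and under section 5.1 the child was not treated. No passage counts such children, says how they enter a rate, or requires that they be reported. The enrollment rule therefore selects on a step of the outcome.

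What is at stake is how the per-subject success rate, and any rate reported for section 4.3, can be read. Leaving out stops for intolerance or movement cannot lower either rate, and a reader could not tell how far it had raised them. There is a smaller safety point. Section 12.0 promises that all adverse events will be reported, but an event during these early steps in a child who is never enrolled may be missing from the as-treated summaries.

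Two things are outside the concern. The per-ear delivery endpoint in section 4.2 may reasonably stay conditional on an attempt. A child whose second ear is abandoned is already enrolled and already fails the both-ears rule.

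**Working it through.** **Step 1: who is in the denominator.**

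| Stage | Section | Child stopped before the first incision |
|---|---|---|
| Eligibility judged | 5.2 (before consent) | Passed |
| Consent signed | 5.2 | Yes |
| Movement control, wax removal, topical anesthetic | 9.0, 11.1.3.1 | Stopped here |
| Incision and attempted delivery | 5.2 | No, so not enrolled |
| As-treated analysis, N = 60 (30 + 30) | 5.1 | Not included |

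Because the analysis N equals the enrollment goal, the natural reading is that recruitment continues until 30 attempted children per group are reached. This is an inference: no section states the per-subject denominator.

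**Step 2: reproduce the plan's own intervals (section 6.0).** For x events in n, the Clopper-Pearson 95% limits are

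- lower = 0.025 quantile of Beta(x, n − x + 1)
- upper = 0.975 quantile of Beta(x + 1, n − x), or 100% when x = n

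With counts rounded to whole ears, all four rows are reproduced:

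| Quantity | x/n (ears) | Limits (%) | Width (points) |
|---|---|---|---|
| Adverse events, overall | 5/120 | 1.4 to 9.5 | 8.1 |
| Adverse events, subgroup | 3/60 | 1.0 to 13.9 | 12.9 |
| Delivery, overall | 114/120 | 89.4 to 98.1 | 8.7 |
| Delivery, subgroup | 57/60 | 86.1 to 99.0 | 12.9 |

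The plan's arithmetic is sound. The issue is only who is counted.

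**Step 3: effect on the per-subject rate.** Let s be the successes among the enrolled children and k the consented children stopped before incision for intolerance or movement. The reported rate is s/60; with the stops counted as failures it is s/(60 + k). In one age group, 30 replaces 60. The documents give neither k nor an expected per-subject rate (the 95% in section 6.0 is per ear). Both s and k are therefore assumptions, with k from 0 to 3.

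| Group | k | x/n (children) | Rate (%) | Exact 95% CI |
|---|---|---|---|---|
| Overall | 0 | 57/60 | 95.0 | 86.1 to 99.0 |
| Overall | 1 | 57/61 | 93.4 | 84.1 to 98.2 |
| Overall | 2 | 57/62 | 91.9 | 82.2 to 97.3 |
| Overall | 3 | 57/63 | 90.5 | 80.4 to 96.4 |
| Overall, no failures | 0 | 60/60 | 100 | 94.0 to 100 |
| Overall, no failures | 3 | 60/63 | 95.2 | 86.7 to 99.0 |
| One age group | 0 | 28/30 | 93.3 | 77.9 to 99.2 |
| One age group | 3 | 28/33 | 84.8 | 68.1 to 94.9 |
| One age group, no failures | 0 | 30/30 | 100 | 88.4 to 100 |
| One age group, no failures | 3 | 30/33 | 90.9 | 75.7 to 98.1 |

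The age-group rows with k = 3 assume that all three stops fall in that one group. None of these per-subject figures applies to a per-ear rate.

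**Step 4: can the earlier 98.9% serve as a benchmark?** Section 1.3 reports office success of 98.9% of cases, from 225 children (209 of them aged 6-24 months) and 437 ears. By ears, 432/437 = 98.86%, which rounds to 98.9%. By children, the nearest counts do not: 222/225 = 98.67%, 223/225 = 99.11%, 206/209 = 98.56%, 207/209 = 99.04%. The other two figures in that section also fit ears: 424/437 = 97.0% and 2/437 = 0.46%. The figure looks per ear, so it is not a benchmark for a per-subject rate.

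**The case against.** The strongest reply is that this is a disclosed design choice. Section 5.2 states the enrollment point openly, section 5.1 declares an as-treated analysis, and section 4.3 speaks of placing tubes with the device, so a rate among children in whom the device was tried fits the wording. Section 5.1 names no separate rate for section 4.3. There is no hypothesis test or performance goal, and no decision threshold would change. The number of stops is entirely assumed.

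The information may also exist already. The Enrollment form is timed before the procedure (section 11.1), and consent documents are monitored 100% (section 17.0). The case report forms are not in the supplied text and may record the reason for a stop. The tolerability videos cover the pre-incision steps. Both anticipated adverse events in Attachment C need an incision or passage of the tube, so the main delivery-related safety rates are untouched.

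Much of this stands. It limits the weight of the point and makes the remedy cheap. It does not answer the point, because none of these provisions puts an early-stopped child into a reported rate. A form completed before the procedure makes a count possible but does not require it. The videos cover only a consenting subset at sites able to record, and no section links them to success. The qualitative review of all data is not said to include children who were never enrolled.

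**Conclusion.** The concern holds and should be fixed. On the most natural reading of sections 3.0, 5.1 and 5.2 together, eligible, consented children stopped before the first incision are absent from the per-subject success rate and from any rate reported for section 4.3. The direction is certain: up or unchanged. The size is not known, and it is zero if no child is stopped. Under the assumed counts, three stops move the overall rate by 95.0 − 90.5 = 4.5 points, or an age-group rate by 93.3 − 84.8 = 8.5 points if all three fall in that group. The conclusion rests on an inferred denominator, so confidence is medium. No threshold is crossed, and the per-ear delivery endpoint is not in question.

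**What to change.** Keep the as-treated analyses as planned and add the following to sections 4.3, 5.1 and 5.2:

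- **Log.** Record every consented, eligible child brought to the procedure room, the reason for any stop before the first incision, and any event before the stop.
- **Report.** Give the number and reasons overall and for ages 2-4 and 5-21, even if the number is zero.
- **Supplementary rate.** Report a per-subject office-success rate with an exact 95% CI. Count each child once, by final office outcome, with stops for intolerance or movement as failures. A child stopped and later treated successfully in the office counts once, as a success, with the earlier stop still listed.
- **List separately, not as failures.** This covers children found after consent to meet exclusion 1 or 2 for a reason other than intolerance or movement during the procedure, and withdrawals of consent or assent unrelated to tolerance.
- **Benchmark.** Do not set the per-subject rate beside the earlier 98.9%, which appears to be per ear.

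The cost is some wording, one log line with a reason, and one supplementary table row per analysis group. No visits or procedures are added. The count may be recoverable from the existing enrollment form and consent monitoring. The downside is that the supplementary rate may be somewhat lower than the as-treated rate, and two rates must be explained.

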13.2 Risks

Previous clinically studies have demonstrated that the risks for this study are no different from those associated with standard tympanostomy procedures.

Potential risks or discomforts associated with any tympanostomy tube surgery include, but are not limited to, the following: otorrhea, acute tube extrusion, chronic tube extrusion, tube dislocating into the middle ear, tube plugging, bleeding, vertigo, nausea, infection, hearing loss, facial nerve injury.

Older children and adults typically receive ear tubes in a clinic setting using only local anesthetic since they can remain still and tolerate the procedure. In this study, movement will be controlled to prevent motion that could interfere with the procedure while the surgical instruments are in the ears. Except for movement, which will be controlled by the nurse and doctor, the researcher and sponsor are not aware of any risks in this study that are different from normal ear tube procedures in an office setting. Methods to control patient movement in this study are no different than those normally used for children treated in the clinic for a procedure such as removal of a foreign body in the ear or nose or remove cerumen, or to perform such routine procedures as flexible nasopharyngoscopy or flexible laryngoscopy in the clinic.

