ATTACHMENT D- Definitions for Additional Events of Interest

| Events | Definition | |
|---|--|--|
| | Infection as defined as: | |
| Infection | Patient has fever > 101 F beyond 24 hours post-surgically (per parent feedback) OR | |
| | Unusual or excessive TM inflammation OR | |
| | Otitis externa | |
| Unintended TM perforation | During the procedure, the surgeon inadvertently creates a perforation in the TM without successfully delivering a tube. | |
| Hearing loss due to damage to | Hearing loss due to procedural damage to the ossicular chain due to the | |
| middle ear structures | tube being placed in the posterior-superior quadrant. | |
| Abrasion of the external auditory canal | Excessive or unusual abrasion to the external auditory canal at time of procedure. | |
| Ear bleeding | Excessive or unusual bleeding in the ear canal or tympanic membrane that requires epinephrine or oxymetazoline at the time of the procedure. | |
| Medialized or partially medialized tube | Ear tube is medialized or partially medialized at follow-up. | |
| Ear Pain | Excessive or unusual ear pain exhibited by the child or reported by the parent or by the child at follow-up. | |
| Lateral displacement of tube | Lateral displacement of tube during deployment | |

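### With no safety set defined, a consented child injured before the first attempted H-TTS delivery falls outside the overall AE rate and the by-type rates for events not specific to delivery

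*Combined protocol and SAP*

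**What the plan says.** - **Who is a subject.** Under 5.2, enrollment needs signed consent and two procedural conditions together: "the incision is made in the tympanic membrane and delivery of the ear tube is attempted with the H-TTS".
- **How many.** Section 3.0 sets the target in enrolled patients: "The goal is to enroll 30 patients in the 2-4 year old group and 30 patients in the 5-21 year old group".
- **What is analyzed.** Section 5.1: "Data from the study will be analyzed on an as-treated basis using a common closing date". It continues: "The analysis outlined below will be completed first on all subjects aged 2 to 21 years (N=60"), followed by the two age groups of 30. The AE rate is among the quantities computed there. As-treated is not defined, and no safety population is named.
- **Safety endpoint.** Section 4.1: "The rate of AEs, and the rates for each specific type of event, will be analyzed". No denominator is given.
- **When exposure starts.** Section 9.0 has movement control where appropriate and topical anesthetic on the tympanic membrane before the H-TTS enters the canal.
- **Which risk is singled out.** Section 13.2 says that the researcher and sponsor know of no risks differing from ordinary office tube placement, with one exception: "Except for movement, which will be controlled by the nurse and doctor".
- **Which injuries are foreseen.** Attachment D includes canal abrasion ("Excessive or unusual abrasion to the external auditory canal at time of procedure") and perforation where "the surgeon inadvertently creates a perforation in the TM without successfully delivering a tube".
- **Reporting.** Section 12.0 requires all AEs to be reported, and 5.1 promises detailed summaries of them. Neither supplies a denominator for patients who are not enrolled.

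**The concern.** A safety rate should start counting when the patient is first exposed. Here the count starts later, at incision plus attempted delivery. A consented child may be restrained, given the anesthetic, have the device in the canal and be hurt, and then have the procedure stopped. That child is not a subject under 5.2. Because the target counts enrolled patients, the child also uses no place in the 30 + 30.

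The omission need not be random. Movement is the risk that 13.2 sets apart, and it is also a plausible reason to stop before delivery is attempted. The rule can therefore leave out patients because the risk under study occurred. At stake are the overall AE rate, the by-type rates for events not specific to delivery, and any summary of events such as canal abrasion.

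**Working it through.** **1. Method and the plan's own figures.** The plan uses two-sided 95% Clopper-Pearson intervals. For x events in n, the lower limit is the 0.025 quantile of Beta(x, n − x + 1), and the upper limit is the 0.975 quantile of Beta(x + 1, n − x). With x = 0 the lower limit is 0 and the upper limit is 1 − 0.025^(1/n).

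The tables in 6.0 reproduce with these whole counts:

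| Row | Count | Computed (%) | Stated (%) |
|---|---|---|---|
| AE, overall | 5/120 ears | 1.37–9.46 | 1.4–9.5 |
| AE, age group | 3/60 ears | 1.04–13.92 | 1.0–13.9 |
| Delivery, overall | 114/120 ears | 89.43–98.14 | 89.4–98.1 |
| Delivery, age group | 57/60 ears | 86.08–98.96 | 86.1–99.0 |

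The expected 4.5% is not a whole count (0.045 × 120 = 5.4; 0.045 × 60 = 2.7), so the AE rows correspond to 4.17% and 5.0%. The stated figures are not in dispute. They show that the plan works from exactly 60 subjects and 120 ears, with no wider set for safety.

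**2. Who can be missed.** Set 5.2 against 9.0:

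- Stopped after movement control, anesthetic or canal entry, with no delivery attempted in either ear: exposed, not enrolled, in no rate.
- Attempted in at least one ear: enrolled. An injury at the other ear stays in the per-subject set.

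**3. Which rates can lose an event.** By the Attachment C definitions, acute extrusion needs a completed incision, and displacement needs a tube to pass through the membrane. Neither can occur in a child stopped earlier. The rates that can lose an event are the overall AE rate and the by-type rates for other events (4.1), and any summary of Attachment D events that precede delivery.

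**4. Size.** The documents give no count of such children, so the additions below are assumptions. The overall AE rate is taken per subject, since 4.1 names no unit.

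| Set | As written | Added children | Result |
|---|---|---|---|
| Overall | 0/60 = 0% (0–5.96) | 1, injured | 1/61 = 1.6% (0.04–8.80) |
| Overall | 0/60 = 0% (0–5.96) | 3, one injured | 1/63 = 1.6% (0.04–8.53) |
| Overall | 0/60 = 0% (0–5.96) | 3, all injured | 3/63 = 4.8% (0.99–13.29) |
| Overall | 3/60 = 5.0% (1.04–13.92) | 1, uninjured | 3/61 = 4.9% (1.03–13.71) |
| One age group | 0/30 = 0% (0–11.57) | 1, injured | 1/31 = 3.2% (0.08–16.70) |

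An injured child raises the rate. An uninjured child who was stopped early slightly lowers a non-zero rate.

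**The case against.** The restriction is inferred. No sentence says that AE rates exclude patients who are not enrolled. Section 12.0 asks for all AEs without limiting this to enrolled patients, and the table in 11.1 times the Enrollment form before the procedure, so a record can exist. Study success rests on a qualitative judgement of all data, with no AE threshold to pass. This stands in part: the event is not necessarily lost from reporting. But the endpoint in 4.1 is a rate, and a listing gives no rate. The restriction remains the natural reading of 3.0, 5.1 and 5.2 together.

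Several stronger readings are tempting, and the documents do not support them:

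- *That every AE rate is affected.* The events 5.1 specifies in detail, extrusion and displacement, cannot be lost this way. A wider denominator would only dilute them and would break the comparison with the expected 4.5% of ears treated.
- *That children who have been cut drop out.* Section 1.2 describes a device that incises and inserts with one push of a lever, so an incision without an attempted delivery is close to an empty class. The perforation category in Attachment D most naturally describes a failed attempt, and that patient is enrolled.
- *That Attachment D rates are shown to be biased downward.* Section 11.1.3.3 says only that these events will be collected, and 5.1 sets out no rate or interval for them specifically.
- *That the effect is shown to be largest at ages 2–4.* That is plausible, but no figure supports it, and 13.2 describes the movement-control methods as those already usual in clinic.

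**Conclusion.** The concern holds for a narrow group: consented children in whom movement control, topical anesthetic or canal entry was started and whose procedure stopped before the first attempted delivery. On the plan's wording, an injury to such a child enters neither the overall AE rate nor the by-type rates for events not specific to delivery, nor any summary of Attachment D events.

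The size is unknown and may be zero. If it is zero, nothing changes. With one such child, injured, and no events among the enrolled, the observed overall rate moves from zero to 1.6%, and the upper limit from 6.0% to 8.8%. The intervals overlap heavily, so the issue is whether an event is counted at all, not precision.

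The conclusion assumes that the 60 subjects in 5.1 are the enrolled patients of 5.2. It does not show that the safety results will be biased. It shows that the plan lets harm related to the risk 13.2 singles out go uncounted. The plan should be changed, but this is a modest correction.

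**What to change.** In 5.1:

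1. Define a safety set of all consented patients in whom movement control, topical anesthetic or H-TTS entry into the canal was started.
2. On that set, compute the overall per-subject AE rate and the summaries of events not specific to delivery, including Attachment D events.
3. Report how many procedures were stopped before the first attempted delivery.
4. Keep the 5.2 set (subjects and ears with an attempted delivery) for the extrusion and displacement rates, the comparison with 4.5% of ears treated, the delivery rate and the 30 + 30 count.

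In 11.1, instruct sites to complete CRF #2 (if an AE occurred) and CRF #5 for every patient in the safety set. This matters for CRF #5, which is now timed to the end of the follow-up visit. The timing of the Enrollment form should be reconciled with 5.2 at the same time.

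The cost is about a paragraph and a form instruction. No extra patients or procedures are needed: these patients are already consented and the forms exist. The downside is that the safety denominator may exceed 60 and the overall AE rate may be slightly less favourable.
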